12.4.5 Primary Efficacy Analyses

The primary efficacy variables (Pre-CAE®) are:

- Change from Baseline to Month 3 in inferior corneal staining score (Ora Calibra® scale) in the study eye
- Change from Baseline to Month 3 in total corneal staining score (Oxford and Ora Calibra® scales) in the study eye
- Change from Baseline to Month 3 in eye dryness measured using a visual analogue scale (VAS)
- Change from Baseline to Month 3 in Total Ocular Surface Disease Index (OSDI) score, and

The primary variables will be summarized as described in [Section 12.4.1](#). The primary efficacy analysis will use the mITT population with LOCF.

Statistical tests will be performed for each AXR-159 Ophthalmic Solution group versus vehicle group at matched dosing frequency (TID or BID). ANCOVA models will be used to compare the change from baseline primary efficacy variables. The ANCOVA models will include terms for baseline value, baseline inferior corneal staining score (ICCS) and baseline eye dryness score as covariates and treatment (AXR-159 or vehicle) as a factor in the model. Pairwise comparisons will be performed for each AXR-159 treatment group versus vehicle using t-tests of the least square means from this model. Two-sided confidence intervals (95%) will be provided for the differences between treatments. As supportive analyses, two-sample t-tests and Wilcoxon rank sum tests will also be conducted.

Details of additional supportive primary efficacy analyses will be provided in the statistical analysis plan.

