a standard deviation of approximately 0.75 in Phase 2. Sample sizes for this study are based on detecting a 0.35 unit difference between the active and vehicle groups, assuming a standard deviation of 0.75. In Stage 1 the number of expected enrolled subjects varies between 43 and 53 subjects in the active group and between 37 and 47 subjects in the vehicle group. In Stage 2 the number of expected enrolled subjects is 60 in the active group and 30 to 60 subjects in the vehicle group. Thus, the combined sample provides between 103 and 113 subjects in the active group and between 67 and 77 subjects in the matching vehicle group or between 97 and 107 subjects in the combined vehicle group. Under these assumptions and allowing a dropout rate of 10%, sample sizes of 93 in the active treatment group and 60 in the vehicle group will yield 80% power to show a significant difference at the $\alpha = 0.05$ level using a two-sample t-test.

6. Data Preparation

The clinical study database for AXR201701 will be developed and tested in iMedNet™ v1.174.2 or higher. iMedNet™ is delivered as a single-instance multi-tenant Software-as-a-Service (SaaS) EDC system and is developed, maintained, and hosted by MedNet Solutions located in Minnetonka, Minnesota. Therefore, over the duration of the study, MedNet Solutions may apply system updates to the EDC system as part of their continuous improvement efforts. The version of the system at the time of the study completion will be recorded on the Study Lock CheckList.

Data from source documents will be entered into the eCRF by site personnel. After data are entered into the clinical study database, electronic edit checks and data review will be performed. All data validation specifications and procedures are detailed in the Data Validation Manual as a separate document. When the database has been declared to be complete and accurate, the database will be locked. Any changes to the database after data have been locked can only be made with the approval of Ora, Inc. and AxeroVision, Inc. in consultation with SDC.

All analyses outlined in this document will be carried out after the following have occurred:

- All data management requirements are met according to SDC standard operating procedures, including data entry, performance of edit and validation checks, documentation and resolution of data queries, and database lock with written authorization provided by appropriate SDC and Sponsor personnel;

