8.3 Definition of Baseline

Baseline measures are defined as the last measure prior to the initiation of study treatment, usually at Day 1. If a measure is taken both pre-CAE® and post-CAE®, the baseline will be the last time point matched value prior to the initiation of study treatment. For post-CAE® measures, this will be at Day -14. For changes from pre-CAE® to post-CAE® post first treatment, the change from pre-CAE® to post-CAE® at Day -14 will be considered the baseline value.

Changes from baseline will be calculated as visit minus baseline and summarized by treatment and visit as described above. Treatment comparisons between an active treatment and vehicle will be calculated as active minus vehicle.

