8.4 Data Analysis Conventions

All data analysis will be performed by Statistics & Data Corporation (SDC) after the study is completed and the database has been locked and released for unmasking. Statistical programming and analyses will be performed using SAS® Version 9.4 or higher. Output will be provided in rich text format (RTF) for tables and portable document format (PDF) for tables, listings, and figures using landscape orientation. All study data will be listed by subject, treatment, and visit (as applicable) based on all randomized subjects unless otherwise specified.

Summaries for continuous and ordinal variables will include the number of observations (n), arithmetic mean, standard deviation (SD), median, minimum, and maximum). Minima and maxima will be reported with the same precision as the raw values; means and medians will be presented to one additional decimal place than reported in the raw values. SDs will be presented to two additional decimal places than reported in the raw values. Summaries for discrete variables will include frequency counts and percentages. All percentages will be rounded to one decimal place (i.e., XX.X%). Differences between active treatment groups and vehicle will be calculated as Active minus Vehicle and change from baseline will be calculated as follow-up visit minus baseline. The baseline measure will be defined as the last non-missing measure prior to initiation of investigational treatment.

Statistical comparisons between each AXR-159 Ophthalmic Solution group will be to the vehicle group at matched dosing frequency (TID or BID). AXR-159 Ophthalmic Solution plus Artificial Tear group will be compared to both AXR-159 Ophthalmic Solution and to the vehicle group at matched dosing frequency.

A final database lock will occur at the completion of Stage 2 and the safety, tolerability, and efficacy data from both Stage 1 and 2 will be analyzed separately and in a combined fashion to fully leverage the advantage of this two-stage study design.

All statistical tests will be two-sided with a significance level of 0.05 ($\alpha = 0.05$) unless otherwise specified. Confidence intervals (CI) for differences between treatment groups will be two-sided at 95% confidence. All p-values will be rounded to four decimal places; p-values less than 0.0001 will be presented as “<0.0001”; p-values greater than 0.9999 will be presented as “>0.9999”.

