13.1.1 PRE-CAE[®] INFERIOR FLUORESCEIN STAINING (ORA CALIBRA[®] SCALE)

Pre-CAE[®] fluorescein staining in the inferior region of the cornea will be graded using the Ora Calibra[®] Corneal and Conjunctival Staining Scale. The Ora Calibra[®] Corneal and Conjunctival Staining Scale ranges from 0 to 4 (half grade increments may be used), where grade 0 = none, 1 = trace, 2 = mild, 3 = moderate, and 4 = severe.

Changes from baseline in the pre-CAE[®] inferior fluorescein staining scores will be summarized at Visit 5 (Day 85 ± 2) by treatment group for the study eye using quantitative summary statistics. Changes from baseline will be compared between each AXR-159 Ophthalmic Solution group versus vehicle group at matched dosing frequency (TID or BID) using an ANCOVA model that adjusts for baseline. Specifically, the ANCOVA model will include terms for baseline inferior corneal staining score (ICCS) and baseline eye dryness score as covariates and treatment group as a factor in the model. The differences in means, two-sided 95% CIs for the difference in means and p-values will be reported. Pairwise t-tests from the ANCOVA model will be used to compare treatment and vehicle groups.

The following SAS code will be used to run the ANCOVA analysis for each of Stage 1 and Stage 2:

```
PROC MIXED DATA = INDATA;
```

```

CLASS TREATMENT;
MODEL CHANGE_ICSS = BASELINE_ICSS BASELINE_EDS TREATMENT
   / SOLUTION COVB;
LSMEANS TREATMENT / CL PDIFF;
ODS OUTPUT LSMEANS = OUTLS DIFFS = OUTDIFFS;
RUN;

```

where

- *TREATMENT* is the name of the treatment group variable
- *BASELINE_ICSS* is the baseline pre-CAE® inferior fluorescein staining score in the study eye
- *BASELINE_EDS* is the baseline pre-CAE® eye dryness score
- *CHANGE_ICSS* is the pre-CAE® inferior fluorescein staining in the study eye at Visit 5 (Day 85 ± 2) – *BASELINE_ICSS*
- *OUTLS* is the name of the output dataset that contains the statistical results for the treatment means from the ANCOVA model
- *OUTDIFFS* is the name of the output dataset that contains the statistical results for the differences in treatment means from the ANCOVA model

T-tests and Wilcoxon rank sum tests will also be conducted as sensitivity analyses to assess robustness of the results.

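### The primary ANCOVAs are valid but leave out the pre-CAE Visit 1 reading of each endpoint, a pre-randomisation covariate already scheduled that could add modest precision

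*SAP*

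**What the plan says.** SAP 8.3 fixes a single baseline: "Baseline measures are defined as the last measure prior to the initiation of study treatment, usually at Day 1". Protocol 12.4.5 builds the primary models on it: "The ANCOVA models will include terms for baseline value, baseline inferior corneal staining score (ICCS) and baseline eye dryness score as covariates". SAP 13.1.1 carries this into inferior staining, where the endpoint's own baseline and the ICCS term coincide: "the ANCOVA model will include terms for baseline inferior corneal staining score (ICCS) and baseline eye dryness score as covariates". SAP 13.1.2, 13.1.3 and 13.1.5 (total Ora staining, Oxford staining, total OSDI) use the endpoint's own baseline plus baseline ICCS and eye dryness. SAP 13.1.4 (VAS dryness) uses baseline dryness and ICCS. None has a Visit 1 term. The PROC MI code in 13.1.1 lists only the baseline and Visit 5 scores.

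Fluorescein staining on both scales, VAS and OSDI are scheduled at Visit 1 before the 90-minute CAE exposure (Protocol 10.3.1.1 and Appendix 1; SAP 3.2) and again at Visit 2. Protocol 7.3 makes inferior Ora staining, VAS dryness and total OSDI entry criteria at both visits, and SAP 4.1 allows randomisation only when all criteria are met at both. The total Ora sum and the Oxford score are not entry criteria, so their Visit 1 values rest on the visit schedule alone.

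**The concern.** A half-grade examiner score or a single VAS mark is a noisy reading of a patient's usual level. A second reading of the same endpoint, also taken before randomisation, would normally explain more of the Month 3 variance. Treatment cannot affect it, so it introduces no bias. A shift in the mean over the vehicle run-in does not change that.

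What is at stake is the width of the confidence intervals, not their validity. Precision is scarcest where the stages are analysed separately, and the Stage 1 results inform futility decisions and the choice of Stage 2 groups. The documents give no reason for leaving Visit 1 out of the primary models.

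**Working it through.** **1. The plan's own figure.** SAP section 5 is "based on detecting a 0.35 unit difference between the active and vehicle groups, assuming a standard deviation of 0.75", and states that "sample sizes of 93 in the active treatment group and 60 in the vehicle group will yield 80% power". Testing is two-sided at 0.05.

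- SE = 0.75 × √(1/93 + 1/60) = 0.1242, and 0.35/0.1242 = 2.818.
- Power = Φ(2.818 − 1.960) = 80.5%; the noncentral t gives 80.0%. The stated 80% reproduces.
- The lower enrolment figures after 10% dropout give 103 × 0.9 = 92.7 and 67 × 0.9 = 60.3, in line with 93 and 60.

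The calculation uses an unadjusted two-sample t-test and claims no gain from covariates.

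**2. Gain with equal correlation r between Visit 1, Day 1 and Month 3 (assumed).** Residual variance relative to total is 1 − r² with Day 1 alone and 1 − 2r²/(1 + r) with both readings. Their ratio is [1 − 2r²/(1 + r)]/(1 − r²). Without entry thresholds:

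| r | variance cut | SE cut | patient equivalent |
|---|---|---|---|
| 0.3 | 5.3% | 2.7% | +5.6% |
| 0.5 | 11.1% | 5.7% | +12.5% |
| 0.7 | 17.0% | 8.9% | +20.4% |

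**3. Entry thresholds.** Selecting on both readings narrows their range and shrinks the gain. In a simulated trivariate normal cut at −0.5 or −1 SD at both visits, the SE ratio runs from 0.985 (r = 0.3) to 0.927 (r = 0.7). In patient equivalents, 1/0.985² = 1.03 and 1/0.927² = 1.16. A second simulation used half-grade scores, entry thresholds and selection of the worse eye on Day 1, with underlying r of 0.5 to 0.7. It gave a variance cut of 6 to 11%.

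**4. Correlation that fades with time.** Write r12, r25 and r15 for Visit 1–Day 1, Day 1–Month 3 and Visit 1–Month 3. Then R² = (r15² + r25² − 2·r15·r25·r12)/(1 − r12²), and the variance ratio is (1 − R²)/(1 − r25²).

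- At 0.6/0.5/0.4, R² = (0.16 + 0.25 − 0.24)/0.64 = 0.2656. The ratio is 0.7344/0.75 = 0.979, so the SE falls 1.0%. With the entry cuts the SE ratio is 0.992 to 0.993.
- If r15 = r12 × r25, Visit 1 adds nothing and the gain is zero.

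**5. Power at 93 v 60, under two readings of 0.75.**

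*As the residual SD of the planned ANCOVA.* Multiplying 0.75 by 0.985 or 0.927 moves the noncentral-t power from 80.0% to 81.1% or 85.6%. With fading correlation it reaches about 80.5%.

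*As the SD of change.* Day 1 adjustment already multiplies the SD by √[(1 + r)/2]. Without entry thresholds, using the normal formula:

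| r | planned SD | planned power | SD with Visit 1 | power with Visit 1 |
|---|---|---|---|---|
| 0.3 | 0.605 | 93.8% | 0.588 | 94.9% |
| 0.5 | 0.650 | 90.2% | 0.612 | 93.2% |
| 0.7 | 0.691 | 86.4% | 0.630 | 91.8% |

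The gain is 1.1 to 5.4 points. Entry thresholds take the lower end of planned power to about 85%. With fading correlation the SD goes from 0.650 to 0.643 and power rises by less than one point.

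**6. Single stages (0.75 as residual SD, same SE ratios, noncentral t).** The largest Stage 1 after 10% dropout (53 and 47 become about 48 v 42) moves from 59% to 60–65%. Stage 2 against a 30-patient matched vehicle (54 v 27) moves from 50% to 51–56%.

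**The case against.** The best case against is that nothing is wrong. Protocol and SAP agree on a pre-specified, valid model with a defined baseline, and SAP 8.5 calls all efficacy analyses exploratory. That stands, and it limits the point to an improvement.

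A reader might infer that standard errors will fall in every primary comparison. They need not. In simulations of the fading case, with entry cuts and a further covariate in the model, the mean SE ratio was 0.998 to 0.999 at 50 v 43, and the estimated SE rose in about 55 to 58% of trials. At 93 v 60 the ratio was 0.995 to 0.997, and the SE rose in about 41 to 46%. If Visit 1 adds nothing, the mean SE rises by 0.3 to 0.6%. These losses are trivial, but the gain is an expectation that depends on the correlations.

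Fading is plausible. Visit 1 to Day 1 is two weeks and Day 1 to Month 3 is twelve. Visit 1 also precedes the vehicle run-in, whereas the other two readings are taken while patients are using drops. The upper end of the range therefore rests on a favourable assumption.

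A reader might also infer that the trial is underpowered, or that 80% is the power of the planned ANCOVA. The SAP gives 0.75 next to a mean change from baseline and uses it in a t-test. The SD of change is thus the more natural reading, and on it the planned model already exceeds 80%.

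Finally, the existing extra Day 1 covariates may absorb part of the gain. This is most likely for Oxford staining, which carries a second corneal grade, and OSDI, which carries a second symptom score. Nor do the entry criteria guarantee a complete Visit 1 value for all five endpoints.

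**Conclusion.** The point holds as a missed efficiency. The five primary models omit a covariate that is already scheduled, is taken before randomisation and cannot bias the comparison.

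The size rests on correlations the documents do not give:

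- **Equal correlation of 0.3 to 0.7, with entry thresholds:** expected SE down about 2 to 7%, worth about 3 to 16% more patients.
- **Correlation fading as 0.6/0.5/0.4:** about 1% or less.
- **Visit 1 uninformative given Day 1:** no gain, and a negligible loss from the extra degree of freedom.

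At 93 v 60, power goes from 80% to about 81–86% if 0.75 is a residual SD. If it is the SD of change, the planned ANCOVA already has about 85–94% and gains about 1 to 5 points, or under one point with fading. The documents do not support calling the planned analysis biased, erroneous or underpowered on this account.

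**What to change.** Before Stage 1 is unmasked:

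- Add the Visit 1 pre-CAE value of the same endpoint as a covariate in the five primary ANCOVAs and their sensitivity versions. Use the same study eye for signs and the subject-level value for VAS and OSDI.
- Keep change from Day 1 as the outcome, so the estimated quantity is unchanged.
- Add the Visit 1 value to the PROC MI variable lists, region by region for total Ora staining.
- State a simple treatment-blind fill-in for a missing Visit 1 value, such as the overall Visit 1 mean or the patient's Day 1 value. PROC MIXED drops records with a missing covariate. Apply the fill-in before PROC MI, which runs separately by treatment group.
- Record the departure from Protocol 12.4.5 in SAP section 18, which now reports no changes.

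The cost is one degree of freedom per model and minor edits to SAP text and code. No new data or visits are needed.

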The primary analysis will be performed on the mITT population with the LOCF imputation method for missing values. For the LOCF analysis, the last value from the previous visits will be carried forward. Only pre-CAE® or non-CAE® time points will be used to impute a missing pre-CAE® value.

As sensitivity analyses, the primary analysis will also be performed on the mITT2 population with LOCF, the PP population with LOCF, the mITT population with observed data only, and the mITT population with MCMC imputation.

The MCMC method will be performed using the SAS procedure PROC MI. The SAS code for obtaining multiple imputation data is:

```

PROC MI DATA = INDATA SEED = SEED_VALUE OUT = OUTDATA NIMPUTE = 20
   MINIMUM = 0 MAXIMUM = 4 ROUND = 0.5;
   BY TREATMENT
   MCMC INITIAL = EM;
   VAR BASELINE_ICSS ICSS;
RUN;

```

where

- *INDATA* is the name of the input dataset
- *OUTDATA* is the name of the output dataset

- *TREATMENT* is the name of the treatment group variable
- *BASELINE_ICSS* is the baseline pre-CAE® inferior fluorescein staining score in the study eye
- *ICSS* is the pre-CAE® inferior fluorescein staining in the study eye at Visit 5 (Day 85 ± 2)

In the above, the random number seed *SEED_VALUE* will be set to 62521 + S, where S = 1 for Stage 1 data analysis, S = 2 for Stage 2 data analysis, and S = 3 for analysis of the combined Stage 1 and Stage 2 data.

After obtaining twenty complete data sets and calculating changes from baseline, the following SAS code will be used to run the ANCOVA model on each data set and combine the results from the twenty analyses:

```

PROC MIXED DATA = OUTDATA;
  BY _IMPUTATION_;
  CLASS TREATMENT;
  MODEL CHANGE_ICSS = BASELINE_ICSS BASELINE_EDS TREATMENT
    / SOLUTION COVB;
  LSMEANS TREATMENT / CL PDIFF;
  ODS OUTPUT LSMEANS = OUTLS DIFFS = OUTDIFFS;
RUN;
PROC SORT DATA=OUTLS; BY TREATMENT _IMPUTATION_; RUN;
PROC MIANALYZE DATA=OUTLS;
  BY TREATMENT;
  MODELEFFECTS ESTIMATE;
  STDERR STDERR;
RUN;

DATA OUTDIFFS;
  SET OUTDIFFS;
  COMPARISON = TREATMENT||' - '||LEFT(_TREATMENT);
RUN;
PROC SORT DATA=OUTDIFFS; BY COMPARISON _IMPUTATION_; RUN;
PROC MIANALYZE DATA=OUTDIFFS;
  BY COMPARISON;
  MODELEFFECTS ESTIMATE;
  STDERR STDERR;
RUN;

```

where

- *TREATMENT* is the name of the treatment group variable
- *BASELINE_ICSS* is the baseline pre-CAE® inferior fluorescein staining score in the study eye
- *BASELINE_EDS* is the baseline pre-CAE® eye dryness score

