- *CHANGE_ICSS* is the pre-CAE® inferior fluorescein staining in the study eye at Visit 5 (Day 85 ± 2) – *BASELINE_ICSS*

- OUTLS is the name of the output dataset that contains the statistical results for the treatment means from the ANCOVA model that is run on each of the twenty imputation datasets
- OUTDIFFS is the name of the output dataset that contains the statistical results for the differences in treatment means from the ANCOVA model that is run on each of the twenty imputation datasets

Similar SAS code will be used to conduct MCMC multiple imputation analysis for t-tests using the same imputation data sets generated above.

Pre-CAE® inferior fluorescein staining changes from baseline in the study eye will be displayed graphically in a bar chart with standard error bars by visit and treatment group based on the ANCOVA analysis.

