13.1.2 PRE-CAE® TOTAL CORNEAL FLUORESCEIN STAINING (ORA CALIBRA® SCALE)

Pre-CAE® fluorescein staining will be graded using the Ora Calibra® Corneal and Conjunctival Staining Scale. The Ora Calibra® Corneal and Conjunctival Staining Scale ranges from 0 to 4 (half grade increments may be used), where grade 0 = none, 1 = trace, 2 = mild, 3 = moderate, and 4 = severe. Staining will be graded in the inferior, superior, corneal, temporal and nasal regions. The total corneal fluorescein staining score is the sum of the scores from the inferior, corneal and superior regions.

Pre-CAE® total corneal fluorescein staining will be analyzed similarly to pre-CAE® inferior fluorescein staining. Pre-CAE® total corneal fluorescein staining changes from baseline in the study eye will be displayed graphically in a bar chart with standard error bars by visit and treatment group based on the ANCOVA analysis. The ANCOVA models, including the ANCOVA model used in the MCMC analysis, will include terms for baseline total corneal staining score, baseline ICCS and baseline eye dryness score as covariates and treatment group as a factor in the model.

LOCF and MCMC imputation will be performed for each region separately, prior to calculating the total corneal fluorescein staining score. The following random number seed values will be used for the MCMC imputations: 62521 + S for inferior region, 38751 + S for central region, 91121 + S for superior region, 22252 + S for temporal region, and 83620 + S for nasal region, where S = 1 for Stage 1 data analysis, S = 2 for Stage 2 data analysis, and S = 3 for analysis of the combined Stage 1 and Stage 2 data.

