13.1.3 PRE-CAE® TOTAL CORNEAL FLUORESCEIN STAINING (OXFORD SCALE)

The Oxford scale ranges from 0 to 5 for the corneal region with higher scores indicating greater staining.

Pre-CAE® total corneal fluorescein staining (Oxford scale) will be analyzed similarly to pre-CAE® inferior fluorescein staining (Ora Calibra® scale). The ANCOVA models, including the ANCOVA model used in

the MCMC analysis, will include terms for baseline total corneal staining score (Oxford scale), baseline inferior corneal staining score (Ora Calibra® scale) and baseline eye dryness score as covariates and treatment group as a factor in the model. Pre-CAE® total corneal fluorescein staining changes from baseline in the study eye will be displayed graphically in a bar chart with standard error bars by visit and treatment group based on the ANCOVA analysis.

The random number seed values that will be used for the MCMC imputations are given by $61521 + S$, where $S = 1$ for Stage 1 data analysis, $S = 2$ for Stage 2 data analysis, and $S = 3$ for analysis of the combined Stage 1 and Stage 2 data.

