13.1.5 PRE-CAE® TOTAL OSDI

The OSDI® is assessed on a scale of 0 to 100, with higher scores representing greater disability. The OSDI® asks the following 12 questions at the subject level:

Have you experienced any of the following during the last week:

- 1) Eyes that are sensitive to light?
- 2) Eyes that feel gritty?
- 3) Painful or sore eyes?
- 4) Blurred vision?
- 5) Poor vision?

Have problems with your eyes limited you in performing any of the following during the last week:

- 6) Reading?
- 7) Driving at night?
- 8) Working with a computer or bank machine (ATM)?

9) Watching TV?

Have your eyes felt uncomfortable in any of the following situations during the last week:

10) Windy conditions?

11) Places or areas with low humidity (very dry)?

12) Areas that are air conditioned?

OSDI[®] will be collected for both eyes pre-CAE[®] at each visit. The 5-unit scale for responses to the OSDI[®] is given by the following: 0 = None of the time, 1 = Some of the time, 2 = Half of the time, 3 = Most of the time and 4 = All of the time. The total OSDI[®] score is calculated by the following:

$$\text{OSDI}^{\circledast} = \frac{(\text{sum of scores}) \times 25}{\# \text{ of questions answered}}$$

Note that the number of questions answered in the denominator should exclude those questions with a response of "N/A".

Pre-CAE[®] Total OSDI[®] will be analyzed similarly to pre-CAE[®] inferior fluorescein staining (Ora Calibra[®] scale). The ANCOVA models, including the ANCOVA model used in the MCMC analysis, will include terms for baseline Total OSDI[®], baseline inferior corneal staining score (Ora Calibra[®] scale) and baseline eye dryness score as covariates and treatment group as a factor in the model. Pre-CAE[®] Total OSDI[®] changes from baseline will be displayed graphically in a bar chart with standard error bars by visit and treatment group based on the ANCOVA analysis.

LOCF and MCMC imputation will be performed for total OSDI score; separate imputations will not be created for each individual question score. The random number seed values that will be used for the MCMC imputations are given by 67521 + S, where S = 1 for Stage 1 data analysis, S = 2 for Stage 2 data analysis, and S = 3 for analysis of the combined Stage 1 and Stage 2 data.

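### The MCMC sensitivity analysis imputes Day 85 from baseline alone, so its ANCOVA nearly repeats the observed-data ANCOVA; imputing Ora regions separately understates the Ora total's SE if regions stay positively correlated given baseline

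*SAP*

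**What the plan says.** SAP 13.1.1 names several sensitivity analyses for the LOCF primary analysis, among them "the mITT population with observed data only, and the mITT population with MCMC imputation". The imputation is PROC MI by treatment group, 20 imputations, with "MINIMUM = 0 MAXIMUM = 4 ROUND = 0.5" and "VAR BASELINE_ICSS ICSS". The second variable is defined as the Visit 5 (Day 85) score, so baseline is the only predictor. After imputation, "the ANCOVA model will include terms for baseline inferior corneal staining score (ICCS) and baseline eye dryness score as covariates", with treatment as a factor. Baseline eye dryness is thus in the analysis model but not in the imputation model. T-tests are covered too: "Similar SAS code will be used to conduct MCMC multiple imputation analysis for t-tests using the same imputation data sets generated above".

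Corneal staining is graded on Day 15 and Day 43 (Protocol 10.3.1.3 and 10.3.1.4), and LOCF carries those values forward.

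For the Ora Calibra total (SAP 13.1.2), "LOCF and MCMC imputation will be performed for each region separately, prior to calculating the total corneal fluorescein staining score", with a different seed for each region. OSDI (SAP 13.1.5) goes the other way: "LOCF and MCMC imputation will be performed for total OSDI score; separate imputations will not be created for each individual question score". The Oxford score "will be analyzed similarly to pre-CAE® inferior fluorescein staining (Ora Calibra® scale"), and VAS and OSDI are handled in the same manner. Those sections give seeds and covariates but no variable list or limits for PROC MI.

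Protocol 12.4.3 only permits MCMC. SAP 8.2 commits to it, and SAP 1 says the SAP's methods supersede the protocol's. SAP 20 plans 15 MCMC tables (five endpoints, each for Stage 1, Stage 2 and combined).

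**The concern.** Observed-data and MCMC analyses are offered as two checks on LOCF. Imputing Day 85 within arm from baseline, then regressing on baseline, places the missing patients on the line already fitted to the completers, plus noise. That adds almost no information. The mITT definition requires at least one post-baseline assessment of some efficacy measure, so most imputed patients will have interim scores that the model ignores. If exits follow those scores, the two analyses share the same bias, and their agreement could be mistaken for robustness.

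The Ora total raises a separate matter. Independent runs discard whatever correlation between regions remains after conditioning on baseline. If that correlation is positive, the summed imputations vary too little and the confidence interval is too narrow.

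**Working it through.** **Inputs from the documents.** Difference 0.35, SD 0.75, 10% dropout, 93 active and 60 vehicle, combined enrolment from 103/67, Stage 2 size 60/30 (SAP 5); 20 imputations, limits 0 to 4, rounding 0.5 (SAP 13.1.1).

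**The plan's own figure.** 0.9 × 103 = 92.7 and 0.9 × 67 = 60.3. SE = 0.75 × √(1/93 + 1/60) = 0.124. 0.35/0.124 = 2.82, and 2.82 − 1.96 = 0.86, giving 80.5% power by the normal approximation and 80.0% by the noncentral t. The stated 80% is reproduced.

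**Assumed, because the documents are silent.** Visit correlations at lags 1/2/3 of 0.60/0.55/0.50 or 0.70/0.60/0.50 (first set only at 60/30); baseline mean 1.75; effects −0.15/−0.25/−0.35 at Days 15/43/85; eye dryness mean 62, SD 14, correlation 0.2 with baseline staining; the exit rules below. There were 1,500 simulated trials per scenario, with scores graded to 0.5 and bounded 0 to 4, imputation by arm, and Rubin's rules.

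**Step 1: overlap of each MCMC analysis with its observed-data counterpart.**

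| MCMC analysis | Active/vehicle | Correlation | Mean gap |
|---|---|---|---|
| ANCOVA as written | 103/67 | 0.993–0.997 | 0.06–0.10 SE (0.007–0.012 units) |
| ANCOVA as written | 60/30 | 0.990–0.995 | 0.08–0.11 SE |
| ANCOVA with Day 15, Day 43 and eye dryness added | 103/67 | 0.964–0.988 | 0.12–0.24 SE |
| t-test as written | 103/67 | 0.966–0.987 | 0.13–0.20 SE |

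The t-test is less redundant because the imputation brings in baseline.

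**Step 2: bias of the MCMC ANCOVA against full data** (true difference about −0.34; a plus sign means attenuation; Monte Carlo error about 0.001).

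| Exit pattern (active/vehicle exits) | As written | With the three variables added |
|---|---|---|
| Random, 10%/10% | +0.001 to +0.002 | – |
| Interim-driven, about equal by arm (9.3/9.7%, 7.5/8.4%) | 0.000 to +0.001 | – |
| Interim-driven, same rule in both arms (7.9/11.6%, 6.6/10.1%) | +0.016, +0.019 (0.14–0.17 SE) | 0.000 |
| Milder rule (10.2/12.6%, 9.7/12.1%) | +0.007 | +0.001 to +0.004 |
| Worsening not recorded before exit (8–10% / 12–15%) | +0.022 to +0.038 | +0.015 to +0.030 |

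Exit probabilities per visit were 0.40 after worsening of at least 1.0, else 0.01 (same rule); 0.15 after at least 0.5, else 0.02 (milder); and 0.50 active or 0.31 vehicle after at least 1.0, else 0.01 (about equal). In the last row exit depended on the Day 85 change: 0.35 if at least 0.5, else 0.03, or 0.50 if at least 1.0, else 0.05. Adding eye dryness alone moved bias by at most 0.001.

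A separate simulation with ungraded scores let exit in the active arm depend on the Day 43 score. Full data gave −0.347, observed data −0.388 and MCMC as written −0.390, a bias of −0.043, now in the drug's favour. Adding Day 43 gave −0.349. At 20% dropout the figures were −0.352, −0.417, −0.420 and −0.350.

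**Step 3: Ora total.** Let f be the missing share, ρ the correlation of Day 85 regional scores given baseline, and k = 1/(1 + 2ρ). With many imputations,

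SE(separate runs)/SE(total imputed directly) = √{(1−f) × [(1−f) + f·k + f·k/(1−f)]}.

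For f = 0.10 and ρ = 0.5, k = 0.5: 0.9 × (0.9 + 0.05 + 0.0556) = 0.905, and the square root is 0.951.

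| f | ρ = 0 | 0.3 | 0.5 | 0.7 |
|---|---|---|---|---|
| 10% | 1.000 | 0.964 | 0.951 | 0.943 |
| 20% | 1.000 | 0.930 | 0.906 | 0.889 |

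Simulation (3,000 trials per cell, random exit, 103/67) agrees: 1.00/0.96/0.95/0.94 and 0.99/0.93/0.90/0.89. Coverage of the 95% interval with separate runs was 94.9/94.2/93.3/93.4% at 10% missing and 94.8/93.9/92.5/92.4% at 20% (Monte Carlo error 0.4 points), against 94.9–95.5% when the total is imputed directly.

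The condition concerns correlation given baseline. With baseline regions correlated 0.7, Day 85 regions correlated 0.175 and residual correlation 0, the simulated ratio was 1.001 at 10% missing and 1.005 at 20%.

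**The case against.** The strongest reply on redundancy is that low missingness causes much of it. After the fix the correlation is still 0.964 to 0.988, so almost any missing-at-random imputation at 10% dropout will sit close to the observed-data analysis. That stands; the fix widens the gap but does not create an unrelated check.

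A reader might infer that the MCMC result is biased against the drug. The documents do not support that. SAP 5 gives one 10% figure, not split by arm; bias is about zero under random or arm-balanced exit, and its sign reverses with the exit pattern (Step 2). A reader might also infer that any positive correlation between regions shrinks the SE. It does not, as the last case in Step 3 shows. At 10% missing and correlation 0.3 the coverage loss is within about two Monte Carlo errors.

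The fix has limits. Protocol 10.2.2 sends patients needing rescue out of the study for worsening signs or symptoms, and Protocol 6.2 says the two correlate poorly, so some exits may not be explained by recorded staining. In the unrecorded-worsening case only about 20 to 30% of the bias goes. Protocol 7.5 asks sites to attempt exit procedures at early discontinuation. A score graded then could be the most informative one available, and the imputation needs a place for it.

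The missing limits for Oxford, VAS and OSDI are a drafting gap. The printed 0 to 4 cannot apply to them, but each scale's range is stated and a programmer would probably fill it in.

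**Conclusion.** Both points hold, at the level of something to consider. As coded, the MCMC ANCOVA adds little to the observed-data ANCOVA and shares any bias that recorded interim scores could remove. No bias is demonstrated: the largest interim-driven cases were +0.019 under the same rule in both arms and −0.043 with exit tied to Day 43 in the active arm, both on assumed exit rules at around 10% dropout. The Ora-total SE is understated by about 4 to 6% at 10% missing and 7 to 11% at 20% if residual regional correlation is 0.3 to 0.7, and not at all if it is zero; the documents give no value.

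Nothing here touches the LOCF primary analysis, and SAP 8.5 calls all efficacy analyses exploratory. The protocol's permissive wording does not make the matter optional, because the SAP commits to these analyses and takes precedence.

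**What to change.** - **Inferior score.** Keep imputation by treatment and use `VAR BASELINE_ICSS BASELINE_EDS ICSS_D15 ICSS_D43 ICSS`, with per-variable limits, for example `MINIMUM = 0 0 0 0 0`, `MAXIMUM = 4 100 4 4 4`, `ROUND = 0.5 1 0.5 0.5 0.5`.
- **Oxford, VAS, OSDI.** Write out the same structure on each scale's own limits: own baseline, Day 15, Day 43 and Day 85, plus the baseline covariates in that endpoint's ANCOVA.
- **Early exits.** Assign any staining or symptom score graded at early exit to the nearest scheduled visit, so that the imputation uses it.
- **Ora total.** Impute the total directly from baseline total, baseline inferior score, baseline eye dryness and the totals at Days 15, 43 and 85, with limits 0 to 12 (three regions × 4). One joint run for the three corneal regions is the alternative.
- **Scope.** State that the analysis covers only missingness explained by recorded scores.

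The cost is a code edit using data already collected. The inferior-score SE moves by −1.5% to +2.4% at 103/67 and by 0 to +4% at 60/30, where coverage is 93.6–95.3% against 93.7–95.4% as written. Direct imputation of the Ora total at 60/30 gave coverage of 94.4–95.7%. The joint run at 60/30 (correlation 0.5) gave 95.1–96.7%, with an SE 2 to 5% larger than imputing the total from baseline, so the direct total is the simpler choice. Directly imputed totals will not equal the sum of separately imputed regions, and the SAP should say so.
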